5.2 Risk Management of the Clinical Device

Although the exclusion criteria mention allergy to methylmethacrylate (a commonly used monomer as a component in many commercial medical, dental, and non-medical applications), this allergy has a low prevalence and materials containing methylmethacrylate or its analogues are managed routinely in dental practices around the world every day. In the case of the rare occurrence of an allergy, patients are isolated immediately from contact, treated using well-known emergency procedures, and recover quickly. In almost every case, a patient knows in advance that they have these types of allergies because they must avoid contacts with a huge number of acrylic materials present normally in world as parts of garments, containers, and common household items. No other adverse effects are known, and none are anticipated.

6 Objectives of the Clinical Investigation

6.1 Objectives

The main purpose of the present study is to evaluate the efficacy of a low viscosity resin (Infiltrant; DMG, Hamburg, Germany) in controlling the regression of White Spot lesions. As a secondary purpose, this study intends to evaluate the usage of SFE for investigation of penetration success and for visualization of early caries.

6.2 Specific Aimes (Primary Endpoints)

6.2.1 Specific Aim I

- Caries arrest evaluated by bitewing radiographs

6.2.2 Specific Aim II

- Confirm optical measurements from SFE laser device correlate with clinical measures

6.3 Secondary Endpoints

- White spot reversal
- Secondary caries
- Post-operative sensitivity
- Color match / surface staining
- Surface quality / texture
- SFE for visualization of early caries and lesion depth assessment

6.4 Study Overview

We propose a randomized, blinded, clinical study of Icon vs. Control (Oral Hygiene Instruction [OHI] and topical fluoridation) as early caries interventions for caries arrest in pediatric populations. 50 non-cavitated early caries lesions, or areas of demineralization, in proximal surfaces of primary molars will be enrolled in this study. Up to 2 early caries lesions may be enrolled per patient, providing the second lesion is in a separate quadrant. Early caries lesions with demineralization seen on occlusal surfaces will be excluded from participation, along with white spot lesions from hypoplasia or fluorosis.

7 Design of the Clinical Investigation

The study will be designed as a controlled, randomized, blinded trial following CONSORT⁴² recommendations as a single center study to investigate the effect of caries infiltration as an alternative treatment option for approximal caries lesions.

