8.2 Clinic visits

A trained study clinician will perform all standard clinical assessments of study lesions in groups 1 and 2, including visual exam and radiograph exam. The study clinician will provide Icon treatment to all study participants randomized to study arm 1 after the radiograph and visual exam. The study clinician will provide oral hygiene instruction and topical fluoridation therapy (Duraphat fluoride varnish) to all study participants randomized to study arm 2 after the radiograph and visual exam.

A trained study clinician will capture the SFE laser optical device image of the study lesions from all study participants. The study examiner will be trained and calibrated by the HPL research team prior to start of study. SFE laser optical device image diagnoses from baseline will be compared to diagnoses from radiograph and visual exams from chart review from the same visit.

Table 8.2 Overview of the procedures during each visit

Procedure	Screening visit	Baseline and Intervention	12 Month Follow-up	24 Month Follow-up
Time		D-0	M 12 (± 3 m)	M 24 (± 3 m)
Patient information	x			
Oral examination	x		x	x
Informed consent	x			
Medical history	x			
Inclusion and exclusion criteria	x		x	x
Selection of eligible lesions	x			
Caries risk assessment	x			
Placing ortho spacers(tx group) D-21 to -7 prior to BI		x	x	x
Randomization	x			
Radiographic examination		x	x	x
Examination by SFE Before spacers placed	(x)*	x		
Examination by SFE Before & After Icon placed		x	x	x
Examination by SFE		x		
Visual Assessment of lesion		x	x	x
Intervention (Infiltration) (EXPERIMENTAL)		x		
Instruction for oral health care		x	x	x
Record of adverse effects		x	x	x
Fluoridation (CONTROL)		x	x	x

*Can be done at screening or baseline appointment

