9.1 Screening Visit

The screening phase allows confirmation of subject eligibility for the trial based in inclusion and exclusion criteria. Screening includes patient information, eligible lesions are evaluated by a study investigator and randomly selected for treatment.

Upon successful completion of the informed consent process by a parent/legal guardian, the participant will be enrolled in the study and randomized to an intervention group. Both groups 1 and 2 will return to clinic 2 weeks prior to intervention baseline visit for a pre-study visit. During this visit orthodontic spacers will be placed interproximally in the study lesion area between the primary molars. The spacer will be maintained in the interproximal area until the patient returns for the intervention baseline visit. The spacer is non-invasive and placed to separate the teeth for better access during the intervention baseline visit for improved visualization and access for Icon/fluoride application. Once the spacer is removed the space will close naturally within 3-4 weeks.

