9.3 Randomization

25 non-cavitated early caries lesions will be randomly assigned, using a random numbers table, to study arm 1) the Icon treatment group; and 25 non-cavitated early caries lesions will be randomly assigned, using a random numbers table, to study arm 2) the Control group (OHI and topical fluoridation).

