9.4 Intervention Visit

9.4.1 Intervention Site “TREATMENT”

All groups will undergo visualization of lesions with radiograph exam, visual exam, and SFE laser optical device exam. 2 weeks prior to the SFE laser optical device exam orthodontic rubber spacers will be inserted next to the study lesions to separate the proximal space for better visualization. The initial SFE exam will occur prior to tooth separation at this visit.

Prior to Icon placement, SFE laser optical device will be performed. The study clinician will provide Icon treatment to all early lesions randomized to study arm 1 after the radiograph and visual exam and a post SFE laser optical device will be performed. The test lesions will be treated using Icon (DMG, Hamburg, Germany) following the instruction for use.

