9.4.2 Intervention Site “CONTROL”

The study clinician will provide oral hygiene instruction and topical fluoridation therapy (Duraphat fluoride varnish; Colgate Oral Pharmaceuticals, New York, NY, United States) to all study participants randomized to study arm 2 after the radiograph, visual exam and SFE Laser Exam. The initial SFE exam will occur at this visit.

Topical fluoridation treatment will be provided is varnish (Duraphat) per manufacturer's instructions.

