14.2 Withdrawal / Dropout of Subjects

Table 14.1.2 Withdrawal and drop-out of subjects separated by level, reason and consequences

Level	Cause	Consequence
Lesion	An allocated lesion progresses radiographically into the middle or inner 1/3 of dentin (criteria D2 and D3).	
The lesion is treated invasively by removing the caries and placing a filling.
 
The case is scored as "progressed" and "failure".

	The patient shows signs of reversible or irreversible pulpitis in an allocated tooth.	
The tooth is treated.
 
The case is scored as "progressed" and "failure".

Patient	The patient shows adverse reactions for one of the study materials.	
Counteractive measures are taken.
 
Unwanted effects are documented in CRF and CEF.
 
The patient is scored as "drop out", data will be assigned as "last observation carried

		forward".
	The patient can not be examined (i.e. x-ray during pregnancy)	The patient is scored as "drop out", data will be assigned as "last observation carried forward".
	One or more allocated lesions have been treated by an external dentist.	The patient is scored as "drop out", will be assigned as "last observation carried forward".
	The patient can not be contacted to make appointments.	The patient is scored as "drop out".
	The patient decides to withdraw his informed consent or study participation.	The patient is scored as "drop out".
Study	One or more patient(s) show severe unwanted side effects to treatment.	Individual counteractive measures are taken. The study is halted.
	More than five patients show unwanted side effects to one treatment or material used.	Individual counteractive measures are taken. The study is halted.

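### The documents contradict each other on whether the child or the lesion is randomized, and the stated 80% power comes from a matched-pairs test that is not the planned unpaired primary test.

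*Combined protocol and SAP*

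**What the plan says.** **Lesions per child.** Protocol Section 6.4 allows one or two: "Up to 2 early caries lesions may be enrolled per patient, providing the second lesion is in a separate quadrant". Sections 7.2.1 and 9.6 agree. Section 7.2 asks for at least one pair of lesions, while Section 7.2.1 asks for one, so the number of two-lesion children is open.

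**Text that randomizes lesions.** Section 9.3: "25 non-cavitated early caries lesions will be randomly assigned" to each arm. Section 9.4.1: "The study clinician will provide Icon treatment to all early lesions randomized to study arm 1". Section 9.1, first paragraph: "eligible lesions are evaluated by a study investigator and randomly selected for treatment".

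**Text that randomizes children.** Section 9.1, second paragraph: "the participant will be enrolled in the study and randomized to an intervention group". Section 8.2: "The study clinician will provide Icon treatment to all study participants randomized to study arm 1". Section 9.4.2 gives the control care "to all study participants randomized to study arm 2 after the radiograph, visual exam and SFE Laser Exam".

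**Sample size and test.** The SAP assumes a 40-point difference in 2-year progression, alpha 0.05 and 80% power. It derives 42 lesions from a matched-pairs t-test and enrols 50 to allow for at least 20% attrition. Its primary test is Fisher's exact test on the proportion of lesions that progressed. Protocol Section 11.4.1 uses a chi-square test for the treatment comparison of caries arrest. Section 11.4.4 carries the last observation forward for dropouts, and Section 14.2 repeats this for several causes of dropout.

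**The concern.** For a child with one lesion the two descriptions of randomization are the same. For a child with two they are different designs: both lesions in one arm, each lesion assigned on its own, or one lesion in each arm. The matched-pairs sample size fits the last of these, yet no visible section says that pairs are split.

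Fisher and chi-square are both unpaired and count lesions as independent. Their type I error depends on which design is run: as for independent lesions if lesions are assigned singly, higher if a child's lesions share an arm, lower if pairs are split. The plan's only power statement belongs to a different test. Two primary tests are also named, which leaves room to choose between them after the data are seen.

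**Working it through.** **Inputs from the documents.** 42 and 50 lesions, 25 per arm; alpha 0.05 (taken as two-sided); a 40-point difference; a control rate of 62% from the one-year primary-molar study that the SAP cites; 20% attrition.

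**Assumptions.** Progression of 62% v 22% for power and 42% in both arms for size; intraclass correlation (ICC) of 0.1 to 0.5; 6, 12 or 24 two-lesion children. The documents give no ICC, no 2-year rate by arm and no count of pairs.

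**1. Reproduce the 42.** For split pairs, n pairs = (1.960 + 0.842)² × V / d², where V = p1(1−p1) + p2(1−p2) − 2ρ√[p1(1−p1)p2(1−p2)].
- With 23% v 63% and ρ = 0: V = 0.1771 + 0.2331 = 0.4102, and n = 7.849 × 0.4102 / 0.16 = 20.1. Rounded up, this is 21 pairs, or 42 lesions.
- With 62% v 22%, the noncentral t at 21 pairs gives 78% power for ρ = 0 and 82% for ρ = 0.1.

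So 42 is a sound figure for a split-pair design.

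**2. Power of the planned tests, independent lesions.** Exact binomial enumeration at 62% v 22%:

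| Lesions per arm | Fisher | Chi-square (uncorrected) |
|---|---|---|
| 21 (42 in all) | 64% | 77% |
| 25 (50 in all) | 79% | 86% |
| 20 (40 in all) | 63% | 74% |

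This shortfall for Fisher does not depend on clustering.

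**3. Attrition.** 50 × 0.80 = 40 lesions, fewer than 42. Excluding dropouts gives the last row. Under LOCF all 50 lesions stay in. If every dropout is carried forward as non-progressed, the rates become 0.62 × 0.8 = 0.496 and 0.22 × 0.8 = 0.176, and Fisher at 25 per arm has 58%. Month-12 progressions carried forward would change that figure.

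**4. Size when both lesions of a child share an arm.** Simulation, 200,000 replicates, 25 lesions per arm, 42% in both arms. The two lesions of a child share one draw with probability equal to the ICC. With independent lesions the exact sizes are 3.1% (Fisher) and 6.2% (chi-square).

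| Two-lesion children | Fisher, ICC 0.1 | Fisher, ICC 0.3-0.5 | Chi-square, ICC 0.1 | Chi-square, ICC 0.3-0.5 |
|---|---|---|---|---|
| 24 | 4.0% | 5.8-7.8% | 7.6% | 10.1-12.9% |
| 12 | 3.5% | 4.3-5.3% | 6.8% | 8.2-9.5% |
| 6 | 3.2% | 3.6-4.1% | 6.5% | 7.1-7.9% |

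**5. Size in the other two designs.** Lesions assigned singly: Fisher 3.0-3.2%, chi-square 6.0-6.2%. Pairs split, ICC 0.3-0.5: Fisher 1.0-0.3% with 24 pairs, 1.9-1.3% with 12 and 2.5-2.1% with 6.

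**The case against.** The best defence is that Section 9.3 is the operative randomization section and assigns lesions. On that reading Fisher keeps its size, the primary analysis need not change, and the shortfall with all 50 lesions is 79% against 80%. This stands, and it limits the point: a reader might infer that the primary test is invalid, and the documents do not support that. Fisher's size under child randomization is at or near 5%, or below it, unless nearly all children give two lesions and the ICC is 0.3 or more. Both quantities are assumed.

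Chi-square appears under a descriptive-statistics heading, and the SAP, which names Fisher, is the more specific source. Chi-square is also already at 6.2% with independent lesions, so not all of its excess comes from clustering. Both points are fair, but the two documents still name different tests.

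Some of the text is weak evidence of conflict. The withdrawal table's wording, "One or more allocated lesions have been treated by an external dentist", fits either unit, because a child's lesions are also allocated when the child is randomized. Part of the design sentence in the Abstract (Section 1.4) is redacted and may have named the design. The contradiction among the visible sections does not depend on that sentence.

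A reader might also take 63% as the plan's power after attrition. It is not, because it drops subjects whom the plan carries forward.

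What the defence does not answer is that participants and lesions are both said to be randomized, and that the 80% belongs to a paired test.

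**Conclusion.** The point holds and should be fixed. The visible text contradicts itself on the randomized unit for two-lesion children, and the stated 80% is not the power of the planned analysis.

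At the SAP's own 42 lesions Fisher has about 64% power. At 50 it has 79%, and after 20% attrition about 63% or 58%, depending on how dropouts are handled. These figures rest on independent lesions and an assumed 62% v 22%. The effect on type I error has no single direction: it is inflated for chi-square and sometimes for Fisher if children are randomized, unchanged from independent lesions if lesions are assigned singly, and conservative for Fisher if pairs are split.

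Two stronger conclusions do not follow. The figure of 42 is not an arithmetical error, since it is reproduced as 21 split pairs. Nor do the documents show that the trial must enrol more lesions; they show that its power is stated for the wrong test.

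**What to change.** 1. In the protocol and SAP, state one randomized unit and how a child's second lesion is allocated. Reconcile protocol Sections 7.2, 7.2.1, 8.2, 9.1, 9.3, 9.4.1, 9.4.2 and 11.4.1 with the SAP's sample-size and analysis text.
2. Name one primary test that matches the unit:
   - Lesions assigned singly: keep Fisher.
   - Children randomized, or only some pairs split: a child-clustered risk difference with a small-sample t reference. Its simulated size is 4.7-5.6% with children randomized and 5.1-5.3% with 12 split pairs.
   - Every child gives a split pair: exact McNemar. It does not suit a mix, because it discards single lesions: with 12 pairs its power is 30-32%, against 84-88% for the clustered risk difference on all 50 lesions.
3. Restate the power of that test at 50 lesions and after attrition, under the missing-data rule actually used. With children randomized and all 50 lesions, the clustered test at ICC 0.3-0.5 has 72-67% power if 24 children give two lesions, 79-76% if 12 do and 81-80% if 6 do. Exact McNemar with 25 split pairs has 74-84% (ICC 0-0.5).

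The cost is wording, modest analysis work and, in most of these cases, a less favourable stated power. No extra lesions, visits or data are needed.

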7.1 Clinical Investigation Protocol

Study enrollment phase includes patient interviews, dental screening and bite-wing radiographs taking.

7.2 Participant Selection

Individuals will be selected among the children who come to the Center for Pediatric Dentistry Seattle, Washington, USA for dental treatment. Healthy children between 6 and 13 years old, presenting at least one pair of early carious lesions in primary molars.

7.2.1 Inclusion Criteria

Children ranging in age from 6-13 years will be eligible to participate. The patients must have a one early caries lesions present in primary molars. Up to 2 early caries lesions may be enrolled per patient, providing the second lesion is in a separate quadrant. All patients must be in good general health and free of any systemic disease or disability, preventing any unnecessary procedures. Patients must be available, as well as can be anticipated, for one-year, and two-year recalls.

Criteria used to assess teeth for acceptance into this study include: (1) teeth fully erupted, in functional occlusion and (2) radiographic evidence of early caries in interproximal areas (1 or 2, Ekstrand's criteria⁹). The patients will be appointed for a pre-study appointment after the legal guardian has undergone the informed consent process for the patients to take part in the study.

Selected teeth will be dried for at least 5 seconds with compressed air and study lesions examined under a standard operating light in the CPD clinic. Visual exam: Ekstrand's criteria⁹ will be used to evaluate and record (Table 8.4.2.1). Study lesions scored in categories 1 or 2 from Ekstrand's criteria will be enrolled in the study.

For radiograph examinations the DMG's criteria⁷ will be used to evaluate and record carious lesions. Study lesions scored in categories E1 and E2 from DMG's criteria⁷ will be enrolled in the study (Table 8.4.2.2 and Figure 3).

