4.3.4 Clinical Studies

Infiltrating a caries lesion is a currently introduced strategy to strengthen damaged tooth structure and to reduce caries progression without any surgical intervention.³⁹⁻⁴⁰ Management of early lesions by infiltrating instead of or postponing restorative treatment would have a great impact towards improving oral health care by means of its non-invasive nature. It will drastically lengthen the life-cycle of a tooth.²⁵ Infiltration would provide a simple and cost-effective management option with the least possible iatrogenic effect and diminished need for future re-treatment due to deteriorating of restoration margins.⁴¹

The promising in vitro results of caries infiltration on extracted teeth were underlined by different clinical trials. Several groups reported slower caries progression in infiltrated sites compared to controls: Radiographically obtained quantification reveals lesion progression in 16% of infiltrated sites compared to 53% for controls after one year and for 24% (infiltration group) and 62% (control) after two years. Recently, the three year follow-up data were published, reporting 32% progression for infiltrated lesion and 70% for controls in this split-mouth study.⁴² Meyer-Lueckel et al. measured progression rates of 7% (infiltrated sites) and 37% (controls) after 18 month in young adults.⁴³ The currently available 3-year data of this study report 4% progression in infiltrated lesion and 42% for controls.⁴⁴ Ekstrand et al. aimed to assess the efficacy of resin-infiltrated lesions covered by fluoride varnish (FV) versus FV treatment only of proximal lesions on deciduous molar teeth in a one year split-mouth study. Radiographically, 23% of the test lesions and 62% of the control lesions had progressed, comparable to the aforementioned results in young adults.⁴⁵

5 Device Risk Analysis and Assessment

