The primary endpoint in this study is the proportion of study lesions that have progressed, whereby a difference in caries progression of 40% after 2 years between resin infiltrated teeth and control will be assumed. This difference is based on a previous infiltration study by Ekstrand et al. [45] who reported a 1-year difference in caries progression in primary teeth of 39% (resin infiltration (23%) vs. control (62%)), which was furthermore comparable to results obtained in young adults. Martignon et al [42] for example reported a difference in caries progression in permanent teeth of 37% and 38% after 1 and 2 years respectively; and Meyer-Lueckel et al. of 30% after 18 months.

Based on an assumed difference in caries progression of 40% between resin infiltrated teeth and control, with alfa = 0.05 and a power of 80% the calculated sample size (t-test; matched pairs) would be 42 lesions to find significant differences. To allow for a potentially attrition rate of at least 20% over a period of 2 years a total of 50 lesions will be included.

Statistical Analysis

All evaluations are performed by one trained examiner. The primary outcome is proportion of study lesions that progressed after 2 years as measured via dental examination and pairwise comparison of radiographs. Differences between groups will be tested using Fisher's exact test.

Secondary outcomes are the proportion of study lesions that progressed after 1 year as well as change in categorical lesion depth (progression to next depth category lesion; E1->E2->D1->D2->filling) after 1 and 2 years as measured by pairwise comparison of radiographs. In addition, the change in categorical lesion depth will be determined via SFE laser optical device imaging after 1 and 2 years and compared to the change in categorical lesion depth as measured by pairwise comparison of radiographs. Differences in categorical lesion depth will be analyzed with Chi-square tests with 95% confidence interval (95% CI) and P = .05.

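### The plan neither requires the study molar to last 24 months nor says how a shed tooth is scored; if its nearest rule is applied, a tooth shed before month 12 counts as not progressed

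*Combined protocol and SAP*

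**What the plan says.** - **Who and which teeth.** Protocol 7.2.1: "Children ranging in age from 6-13 years will be eligible to participate". Sections 6.4 and 11.2 place the lesions on proximal surfaces of primary molars. A child entering at 13 would be 15 at the last visit.
- **Tooth-level entry rules.** Section 7.2.1 asks for full eruption, functional occlusion and an early lesion score (Ekstrand 1 or 2; radiographic E1 or E2). The exclusions in 7.2.2 cover sensitivity, poor access and lesion type. None concerns how long the tooth will stay in the mouth.
- **Availability.** The only durability rule is about the child: "Patients must be available, as well as can be anticipated, for one-year, and two-year recalls".
- **Endpoint.** The SAP's primary outcome is the proportion of lesions progressed after two years, tested with Fisher's exact test. Section 9.5 sets visits at 12 and 24 months, each within 3 months.
- **Loss of a lesion.** Table 14.1.2 (section 14.2) has two lesion-level rows: progression to D2 or D3, and pulpitis. The closest patient-level row has the cause "The patient can not be examined (i.e. x-ray during pregnancy"), and its consequence is drop-out with LOCF. Section 11.4.4 assigns LOCF to dropouts generally and asserts that data will be missing at random.
- **Planning.** In the SAP, "a difference in caries progression of 40% after 2 years between resin infiltrated teeth and control will be assumed". The primary-tooth source, described in 4.3.4, studied "proximal lesions on deciduous molar teeth in a one year split-mouth study".

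**The concern.** Primary molars are deciduous teeth, so some may be shed before the 24-month reading. The plan recognises that the child must be available for two years but makes no matching demand on the tooth. The cited primary-tooth trial ran for one year, so it does not show that such teeth can be followed for two.

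When a study tooth is shed, the investigator has no row to apply. The nearest one leads to LOCF. For a tooth with no follow-up reading, that means carrying forward a baseline score which, by the entry rules, is always unprogressed. At stake is a downward bias in both recorded progression rates and, for early shedding, in the difference between arms. That costs power for the SAP's difference test. It also leans towards Hypothesis I in 4.2.1, under which Icon and the preventive regimen perform alike, so a null result could be misread as support.

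**Working it through.** **The plan's own figure.** The SAP says "the calculated sample size (t-test; matched pairs) would be 42 lesions", "with alfa = 0.05 and a power of 80"%. Sidedness and arm rates are not stated. A two-sided, unpooled two-proportion formula reaches 42:

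n per arm = [p1(1−p1) + p2(1−p2)] × (1.960 + 0.842)² / (p1−p2)²

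- 63% vs 23%: (0.2331 + 0.1771) × 7.849 / 0.16 = 20.1, so 21 per arm, 42 in total.
- 62% vs 22%: (0.2356 + 0.1716) × 7.849 / 0.16 = 19.98, so 20 per arm, 40 in total.

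A paired t-test with standardized effect 0.4 gives 41 pairs one-sided and 52 two-sided. The documents do not say which method was used, and the rest of this point does not depend on it.

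**Inputs for the shedding check.**

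- Control rate 62%: SAP, primary-tooth trial.
- Icon rate 22%: 62% less the SAP's assumed 40 points.
- 25 lesions per arm: section 9.3.
- Share s shed before month 12: **assumed**, equal in both arms and unrelated to progression.

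**Shed before month 12.** Only the E1 or E2 baseline exists, so LOCF records no progression. Recorded rates are 62(1−s)% and 22(1−s)%, and the difference is 40(1−s) points. Fisher power (two-sided, 0.05) is by exact enumeration at 25 per arm.

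| s | Control | Icon | Difference (points) | Power |
|---|---|---|---|---|
| 0% | 62.0% | 22.0% | 40 | 0.79 |
| 10% | 55.8% | 19.8% | 36 | 0.69 |
| 20% | 49.6% | 17.6% | 32 | 0.58 |
| 30% | 43.4% | 15.4% | 28 | 0.47 |
| 50% | 31.0% | 11.0% | 20 | 0.29 |

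**Shed between months 12 and 24.** Here the 12-month status is carried forward. The only trial for which the documents give both one- and two-year rates (4.3.4) has 53% vs 16% and then 62% vs 24%. The SAP describes it as a trial in permanent teeth, so this is an illustration.

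- Control: 62(1−s) + 53s; Icon: 24(1−s) + 16s.
- s = 10%: 61.1% vs 23.2%, difference 37.9 points.
- s = 20%: 60.2% vs 22.4%, difference 37.8 points.
- s = 50%: 57.5% vs 20.0%, difference 37.5 points.

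With none shed the difference is 38 points. Both rates are understated, but the difference barely moves.

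**A related inconsistency.** Section 9.5 ends participation when a lesion moves from E2 to D, whereas Table 14.1.2 withdraws a lesion only at D2 or D3. Which lesions are still in follow-up after month 12, and so could be shed, depends on how these passages are reconciled.

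**The case against.** The strongest reply is that no passage prescribes LOCF for a shed tooth. Section 11.4.4 speaks of dropouts, and Table 14.1.2 scores drop-out by patient. A child who attends with one study tooth shed and a second still in place is not clearly a dropout. This stands: the bias is conditional on the nearest rule being applied. But the alternative is that the plan assigns no outcome at all, which is also a gap.

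Three further readings are tempting and are not supported.

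- A reader might infer that shedding was left out of the attrition allowance. The SAP allows at least 20% over two years without itemising it, so tooth loss may or may not be included.
- A reader might add that losing more than 8 of 50 lesions (16%) leaves fewer than 42. Under LOCF a shed lesion stays in the denominator, so the same lesion cannot be counted as both lost and imputed.
- A reader might conclude that every shed tooth pulls the arms together. The calculation shows this only for shedding before the first follow-up.

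It is also fair to say that the size has no anchor in the documents. They give no shedding ages or rates, and the ages actually enrolled are unknown. The CRF appendix is not in the supplied text, so a code for a shed tooth cannot be ruled out.

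**Conclusion.** The concern holds in a conditional form. The plan admits deciduous teeth to a 24-month endpoint with no retention criterion and no rule for a shed tooth. If the nearest rule is applied, teeth shed before month 12 are scored as not progressed. With 10% or 20% shed in that period, the recorded difference falls from 40 to 36 or 32 points and power from about 0.79 to 0.69 or 0.58.

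These figures rest on assumed shedding rates, equal shedding in the two arms, shedding unrelated to progression, and rates of 62% and 22%. They show sensitivity and do not forecast how many teeth will be lost. The gap should be closed because it is foreseeable and cheap to fix, not because the documents show the loss will be large.

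**What to change.** 1. **Section 7.2.1, tooth criteria.** Add that the study molar is expected, in the investigator's judgement at screening, to remain in place through the 24-month visit. No extra radiograph is needed.
2. **Table 14.1.2, lesion level.** Add a row: a study tooth shed without recorded progression is classed as missing at 24 months and is not carried forward as not progressed. Align 11.4.4 with it.
3. **SAP.** Keep Fisher's exact test, on lesions with an observed outcome. Show LOCF as a sensitivity analysis and report the number shed by arm and by visit interval. Interval-censored models or multiple imputation would be heavy for 50 lesions.

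**Cost.** Some older children become ineligible, and shed lesions leave the primary denominator. The new row removes the early-shedding bias but does not restore the lost information. With 22 or 20 observed lesions per arm (roughly 10% or 20% shed), power at 62% vs 22% is about 0.68 or 0.63. The entry criterion is what protects power.

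For late shedding, the observed-outcome analysis errs slightly the other way, because lesions already progressed are kept and unprogressed ones drop out. On the 4.3.4 rates, with 20% of lesions unprogressed at month 12 then shed:

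- Control: 60.2 / (100 − 0.2 × 47) = 66.4%.
- Icon: 22.4 / (100 − 0.2 × 84) = 26.9%.
- Difference: 39.5 points, against 38.

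This is why both analyses should be shown.
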